3. STUDY DESIGN

This study is funded through a R61/R33 phased award from the NIH HEAL Initiative. The R61 Phase 1 Specific Aims are as follows. In preparation for a larger scale, pragmatic 2x2 factorial trial, we aim to:

1. Refine and manualize IGMV in English and Spanish with stakeholder input and informed by relevant theory.
2. Test randomization procedures, contamination, and intervention fidelity in 40 patients with chronic pain.
3. Determine if there is preliminary evidence for our hypothesized mechanisms of action on improved pain management. We will collect and analyze data on pain outcomes, social isolation, and intersectional stigma.

Here we focus on procedures for specific aim 2, a pilot trial designed to assess the feasibility of key study design procedures for a larger trial.

- We will use a 2x2 factorial randomized clinical trial design.
- The primary feasibility outcome for the study is randomization of participants. The secondary feasibility outcomes include participant retention, intervention fidelity, and intervention adherence. We will also assess degree of bias and contamination between study groups.
- We will also assess quality and variability of data on patient-reported pain-related outcomes. These include pain interference, social isolation, average weekly pain severity, social support for chronic pain, health-related quality of life, depressive symptoms, anxiety, sleep disturbance, internalized stigma of chronic pain, and pain self-efficacy.
- Study population will consist of adult patients 18 years of age and older who have painful diabetic neuropathy and have been seen for their diabetes at SFGH clinics within the past year. Forty participants will be enrolled and randomized to four arms (10 in each group): (a) usual care, waitlist comparison, (b) usual care combined with group acupuncture once weekly, (c) usual care with integrative group medical visits, (d) usual care with group

acupuncture and integrative group medical visits. Participants, practitioners, and assessors will not be blinded. The statistician will be blinded to participant assignment.

- All study procedures will take place at the UCSF Osher Center for Integrative Health and at the SFHN Castro Mission Health Center. Recruitment efforts will be through the Tom Waddell Urban Health Clinic, Castro Mission Health Center, and the Family Health Center.

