6.2 Patient-reported Outcomes

Pain-related outcomes of interest include:

- Pain interference from baseline to three months, measured using an eight-item survey of the NIH Patient Reported Outcomes Measurement Information System (PROMIS).²⁹ Items assess the extent that pain interferes with physical, cognitive, emotional, and recreational activities.
- Social isolation, collected using another NIH PROMIS measure, with an eight-item scale on lacking companionship, feeling left out, and feeling isolated.³⁰
- We will also assess intervention effects on pain intensity, physical functioning, depression, and anxiety using NIH PROMIS measures.³¹⁻³⁴
- Additional aspects of health-related quality of life associated with chronic pain will be collected using NIH PROMIS measures for sleep, social functioning, global physical, mental, and social well-being.
- Participant ratings of global improvement. A single item, 7 point rating on the Patient Global Impression of Change scale will assess minimal clinically important difference in changes in participants' pain.³⁵
- Pain beliefs and attitudes will be assessed with scales for pain catastrophizing³⁶ and pain self-efficacy.^{37,38}
- Social Support in Chronic Pain, a 6-item measure of perceived support related to pain.³⁹
- Internalized Stigma of Chronic Pain (ISCP) scale, 21 items with five subscales on enacted and internalized chronic pain stigma: alienation, stereotype endorsement, discrimination experience, social withdrawal, and stigma resistance (Cronbach's $\alpha = 0.724$).⁴¹ Prior research has documented an association between this measure and pain-related cognitive functioning, such as pain self-efficacy and pain catastrophizing.⁴¹
- Intersectional Discrimination Index measures anticipated, day-to-day, and major discrimination that do not focus on a single axis of discrimination (e.g., racism, homophobia) to capture intersectional categories.⁴²
- Descriptive covariates collected at baseline will include: socio-demographic variables (age,

sex, race/ethnicity, place of birth, level of education, household income, marital status, employment status, and health insurance status) and a substance use screener (using HEAL CDE). Clinical data including chronic pain diagnosis, concomitant conditions, medications, and treatments received for pain will be obtained from participants' medical record.

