9. STATISTICAL CONSIDERATIONS

9.1 Sample Size Rationale

The study will enroll 40 participants. As a small pilot study designed to pilot the refined intervention, we did not conduct a formal power calculation but instead used a confidence interval approach to determine sample size, based on current recommendations for small samples. Findings from the pilot study are intended to help plan for a future trial by estimating key parameters. However, small trials often overestimate treatment effects and the convention of basing power calculations on pilot trials has received considerable scrutiny (Kraemer, 2006). Our approach will be to determine whether the effect size from the pilot is clinically meaningful (i.e., within an 80% confidence interval of a pre-determined effect size) and justifies proceeding with future research. To determine this, Cocks and Torgenson (2013) recommend that a pilot sample size should be at least 9% of the sample size of the planned main study.

Based on data of minimally important differences for PROMIS pain measures, our main study would aim to detect a standardized effect size of 0.25. Using our pilot data to estimate within group correlation and a sample size calculator designed for individually randomized group trials, we estimated a sample size of 360. Using Cocks and Torgenson's method, the corresponding pilot sample size should be at least 32. Using an estimated attrition of 20%, we aim to enroll 40 participants. With 20 participants randomized to each of the study interventions, we will have sufficient power to determine if the effect size estimated from the pilot is within the range of clinical significance using a one-sided 80% confidence interval. If the estimated effect is zero or less, the upper 80% CI will not contain our target effect size of 0.25, and we would not proceed with a main study. If the estimated effect size from the pilot is larger than zero, and the study procedures are feasible and acceptable, then we would have sufficient preliminary data to proceed with the main study.

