9.2 Statistical Analysis Plan

Descriptive analyses

Baseline characteristics of participants, including sociodemographics and health condition variables, will be summarized to determine sample generalizability, and compared to assess group equivalency. We will look at summary statistics for data cleaning (e.g., means, ranges)

and then consider distributions by randomized arm as a check of balanced distribution across groups.

Analysis of Feasibility. Feasibility outcomes will be analyzed by computing percentages, with 95% confidence intervals, of rates of retention and enrollment. We will also conduct a thematic analysis of qualitative responses on participants' experiences with the study and acceptability of group acupuncture.

Assessment of implementation, defined as quality and consistency of the intervention delivery across staff, will be focused on evaluating core components and content of IGMV and parameters in STRICTA guidelines for group acupuncture. IGMV facilitators will complete a short survey after each session documenting content and time spent on each component. Acupuncturists will complete charting for each treatment provided.

Analysis of Patient-Reported Outcome Measures. This study is powered to assess exploratory effects and pilot feasibility, not for confirmatory analysis. Nonetheless, we will analyze clinical outcomes in a manner similar to that planned for the main study to make a preliminary assessment of the strength of the effects; to identify any unexpected issues with missing data, skewed distributions, or outliers; and to refine the statistical analysis plan. Relative (mean \pm SD) measures of effect sizes will be calculated as change from baseline to post-intervention for all outcome variables. Planned analyses include: within group changes from baseline to Week 12, group acupuncture vs. no acupuncture, and IGMV vs. no IGMV.

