Treatment effects will be estimated using a repeated measures ANCOVA approach. The framework is similar to a linear mixed models but it includes the baseline of the outcome as a covariate (and omits the baseline from the outcome vector), and the models will include indicators for assignment to acupuncture, IGMV, a categorical variable for time, and interactions between treatment indicators and time, as well as random intercepts for person nested within group to account for within-group and within-patient correlation of the repeated measures. Models with a three-way interaction between the two treatment indicators and time will be evaluated as a first step to assess for synergy between IGMV and group acupuncture. We will also calculate an interaction ratio to assess clinically meaningful antagonism or synergy between the two interventions, specified as interaction ratios of ≤ 0.80 or ≥ 1.25 .⁴⁶ If there is evidence of interaction, we will assess marginal effects of each intervention. If no evidence of synergy is identified, we will proceed with models that omit the three-way interaction term, to instead focus on main effects of each treatment type. This approach will optimally weight data for patients with different numbers of responses, and will provide valid estimates in the presence of missing data under relatively mild assumptions about how the missing data arise.⁴⁷ We will conduct intent-to-treat, per protocol, and complier average causal effects analyses; and exploratory as treated analysis (receipt of any group integrative health intervention and dose-response based on number of sessions attended). Outcomes will be normalized as needed to meet model assumptions; for outcomes which do not meet distributional assumptions of normality, other generalized linear mixed models or non-parametric approaches such as Kruskal-Wallis tests will be used. Secondary outcomes will also be analyzed using this approach.

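### The interaction rules in section 9.2 overlap for antagonism, send a found interaction to effects that average over it, and label a ratio clinically meaningful without restating its formula, scale or confidence interval

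*Combined protocol and SAP*

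**What the plan says.** Section 9.2 first fits a model with a three-way term (acupuncture, IGMV, time) to look for synergy. It adds: "We will also calculate an interaction ratio to assess clinically meaningful antagonism or synergy between the two interventions". The cut-offs follow, with a citation of reference 46, and are worded in this way: "specified as interaction ratios of ≤ 0.80 or ≥ 1.25". After that come two conditional sentences. The first is "If there is evidence of interaction, we will assess marginal effects of each intervention". The second is "If no evidence of synergy is identified, we will proceed with models that omit the three-way interaction term", after which the main effects become the focus.

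Earlier in section 9.2 the comparisons are listed without any condition: "Planned analyses include: within group changes from baseline to Week 12, group acupuncture vs. no acupuncture, and IGMV vs. no IGMV". Section 1.2 commits to a factorial analysis both of the margins and of the cells of the 2x2 table. Section 9.1 gives the planning effect: "our main study would aim to detect a standardized effect size of 0.25". Section 9.2 calls the patient-reported analysis exploratory and gives refinement of the SAP as one of its purposes.

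The outcomes point in both directions. For pain interference (section 6.2), "Items assess the extent that pain interferes with physical, cognitive, emotional, and recreational activities", so a higher score is worse. The list in section 3 includes "depressive symptoms, anxiety, sleep disturbance, internalized stigma of chronic pain, and pain self-efficacy", and for pain self-efficacy a higher score is better.

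**The concern.** Three things do not fit together.

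1. **Triggers.** The two conditions are not complements. Antagonism is an interaction, and it is also an absence of synergy. The plan does not say whether the ratio or the model term supplies the evidence, and it gives no criterion for either.
2. **Destination.** When an interaction is found, the effect of each treatment depends on the other, so the informative quantities are the cell contrasts. The interaction branch names marginal effects instead.
3. **Label.** The words clinically meaningful are attached to a ratio whose formula, scale and interval are not restated. What the cut-offs mean depends on the formula.

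At stake is the exploratory report. It could drop the interaction term when antagonism is present, or call noise a clinically meaningful synergy or antagonism. Because the analysis is meant to resemble the one planned for the main study, the rule could be carried forward.

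**Working it through.** **Cell size, from the plan's own figures.** Section 9.1: 0.09 x 360 = 32.4, given as 32; 32 / (1 - 0.20) = 40, which reproduces the enrolment target. Section 3 has four equal arms, so there are 32 / 4 = 8 completers per cell.

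**Triggers set side by side.**

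| Finding | Interaction branch | No-synergy branch |
|---|---|---|
| None | not met | met |
| Synergy | met | not met |
| Antagonism | met | met |

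**What the interaction branch delivers.** Write U, A, G and B for the means under usual care, acupuncture only, IGMV only and both. The interaction is I = B - A - G + U. The acupuncture margin is ½[(A - U) + (B - G)] = (A - U) + I/2. In a balanced 2x2 this is the same contrast as the main effect in the other branch. Example: if acupuncture alone gives 0.25 SD and I = -0.25 SD, its effect is 0.25 SD without IGMV and 0 with it, and the margin reports 0.125 SD, which is neither.

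**What the cut-offs mean under candidate formulas.** None of these is stated in the plan. Assume single effects of 0.25 SD.

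- Simple ratio, (B - G)/(A - U) = (0.25 + I)/0.25. It reaches 0.80 at I = -0.05 SD and 1.25 at I = +0.0625 SD.
- Combined ratio, (B - U)/[(A - U) + (G - U)] = (0.50 + I)/0.50. It reaches the cut-offs at I = -0.10 and +0.125 SD.
- Ratio of mean scores, (B x U)/(A x G), higher score worse, assumed mean 60 and SD 10. Then A = G = 57.5 and A x G = 3306.25. With no interaction B = 55 and the ratio is 0.998. With 0.25 SD synergy B = 52.5 and the ratio is 0.953, so synergy moves it toward 0.80. Reaching 0.80 needs B = 44.08, a synergy of (55 - 44.08)/10 = 1.09 SD. Reaching 1.25 needs B = 68.88, an antagonism of 1.39 SD.

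**How often a point-estimate cut would flag.** I simulated 1,000,000 sets of four independent normal cell means with 8 per cell, residual SD √(1 - r²) and no clustering, where r is the assumed baseline correlation. One follow-up survey is taken, as in sections 1.2 and 4.4, so the three-way term reduces to acupuncture x IGMV.

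| Reading | r | No interaction | 0.25 SD synergy |
|---|---|---|---|
| Simple ratio | 0 | 91% | 90% |
| Simple ratio | 0.7 | 90% | 88% |
| Combined ratio | 0 | 85% | 82% |
| Combined ratio | 0.7 | 82% | 77% |
| Mean scores | 0 | 7% | 10% |
| Mean scores | 0.7 | 1% | 3% |

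For the two ratios of effects, the 1.25-or-more label alone rises from 20-27% to 28-40%. Under true synergy, 40-58% of pilots fall at 0.80 or below, and 20-37 percentage points of that are negative ratios. Setting negative ratios aside leaves 77-85% flagged with no interaction and 72-84% with synergy.

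The mean-score ratio flags 41-44% at a 1 SD interaction and 76-84% at 1.5 SD. The mean of 60 is my assumption. Over means 55 to 65 the flag rate is about 1-10% with no interaction, 2-13% at 0.25 SD, and roughly a third to a half at 1 SD.

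**If the model term decides instead.** The standard error of I is √(4/8) = 0.707 SD at r = 0, and 0.707 x √(1 - 0.49) = 0.505 SD at r = 0.7. The 95% half-widths are 1.45 SD (28 df) and 1.04 SD (27 df). Power for 0.25 SD at two-sided 5% is 6.3% and 7.7%.

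**The case against.** The best defence is that this is a declared exploratory pilot. Low precision for an interaction is expected at 8 per cell under any method. A reader might infer that this imprecision is the error. The documents do not support that: section 9.2 disclaims confirmatory analysis, and the 0.25 SD interaction used above is my benchmark, since section 9.1 gives 0.25 as the target effect and not as an interaction size.

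A reader might also infer that the ratio has no definition or direction at all. That goes too far. Reference 46 is cited at the cut-offs and may define it, and the word order pairs 0.80 or less with antagonism. What stands is that the plan does not restate the definition or tie it to outcome coding. On a ratio of mean scores the pairing would reverse where higher is worse. Section 9.2 does express effect sizes as change from baseline, but it does not link that scale to the ratio.

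Nor can one conclude that cell effects will go unreported. Section 1.2 commits to them, the first-step model could yield them, and the within-group changes in section 9.2 may cover change within each cell. Still, section 9.2 names no between-cell treatment contrast. The two marginal comparisons are already planned without a condition, so part of the remedy is in place.

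Finally, the flag rates depend on formulas the plan does not state. That is a fair limit on the numbers. It does not touch the overlap of the triggers or the destination of the interaction branch, which need no simulation.

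**Conclusion.** The point holds, as a minor one. The overlap for antagonism follows from the text alone. The mismatch between a found interaction and marginal effects follows if marginal has the sense used in section 1.2; if effects at each level of the other treatment were meant, the text should say so.

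The label is the part that depends on assumptions. Under a ratio of effects used as a point-estimate cut, it is applied to most pilots whether or not a 0.25 SD synergy exists, so it would be attached mostly to noise. Under a ratio of mean scores it is rarely applied and still misses more than half of 1 SD interactions, so it would be wrong to say that this reading reliably separates an interaction of that size. Neither reading tells no interaction from one of 0.25 SD. These rates assume 8 per cell, single effects of 0.25 SD, baseline correlation 0 to 0.7 and no clustering.

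The consequence is limited to the exploratory report and to what is carried into the main-study SAP. The primary feasibility outcome and the proceed rule in section 9.1 do not use interaction.

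**What to change.** - Use one word, interaction, in both conditional sentences, and do not let the result choose the model.
- Always report the interaction contrast (both - acupuncture only - IGMV only + usual care) on the outcome scale with its confidence interval.
- Beside it, report the two marginal effects already listed in section 9.2, and the contrasts of acupuncture only, IGMV only and both against usual care, which section 1.2 implies.
- If the ratio is kept, report it as description, with its formula, scale, outcome coding and confidence interval. Do not attach a clinically meaningful label to its point estimate.

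The cost is SAP wording and one more table. The interaction interval will be visibly wide, about ±1.0 to ±1.45 SD, and there will be no yes/no claim of synergy. That imprecision is present under the current rules too; the interval shows it.

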10. DATA COLLECTION AND QUALITY ASSURANCE

10.1 Data Collection Forms

The Investigator will prepare and maintain adequate and accurate source documents designed to record all observations and other pertinent data for each subject in the

study. Study personnel will enter data from source documents corresponding to a subject's visit into the protocol-specific electronic Case Report Form (eCRF) when the information corresponding to that visit is available. Subjects will not be identified by name in the study database or on any study documents to be collected by the Sponsor (or designee), but will be identified by a subject number. If a correction is required for an eCRF, the time and date stamps track the person entering or updating eCRF data and creates an electronic audit trail.

The Investigator is responsible for all information collected on subjects enrolled in this study. All data collected during the course of this study must be reviewed and verified for completeness and accuracy by the Investigator.

10.2 Data Management

The data will be entered into a validated database. The Data Management group will be responsible for data processing, in accordance with procedural documentation. Database lock will occur once quality assurance procedures have been completed.

All procedures for the handling and analysis of data will be conducted using good computing practices meeting FDA guidelines for the handling and analysis of data for clinical trials.

10.3 Quality Assurance

10.3.1 Training

All UCSF Key Personnel conducting human research are required to complete human subjects protection training through an online program called the Collaborative Institutional Training Initiative (CITI). UCSF Key Personnel are defined as all individuals who contribute in a substantive way to the scientific development or execution of the study at or on behalf of UCSF. In addition, UCSF IRB considers individuals who obtain informed consent to be Key Personnel. The CITI course includes an overview of the regulations that govern human subjects research, as well as training modules on the Health Insurance Portability and Accountability Act as it applies to research. To supplement CITI modules, study staff will also receive online training in Good Clinical Practice, Responsible Conduct in Research, and more detailed HIPAA privacy and information security training.

10.3.2 Quality Control Committee

The quality control committee will consist of [name] (PI), [name] (study statistician) and [name] (project manager). [name] will report on metrics described in 10.3.3 on a weekly basis with study staff. [name], [name], and [name] will regularly review quality control reports on a quarterly basis and more frequently as needed should any issues or questions arise.

10.3.3 Protocol Deviations

At each study encounter, study staff will complete forms documenting adherence and deviation with key aspects of the study protocol. The Principal Investigator will review the forms on a monthly basis to evaluate any deviations from the study protocol. In addition, protocol deviations will be discussed at regularly scheduled study meetings.

Practitioner adherence to the study manual will also be evaluated by review of practitioner clinic notes, observation of clinic visits, and interviews with practitioners

at the completion of each cohort. We will observe three study visits per cohort (i.e., monthly over the twelve weeks of acupuncture visits). Deviation from the study protocol will be defined as any diagnosis or acupuncture point that is not described in the study manual. All deviations will be documented in the Manual of Procedures.

